10.1.4. Sensitivity Analyses

The following sensitivity analyses will be performed for the primary endpoint with the FAS:

1. Pattern mixture multiple imputation. This will assume that missing data after treatment discontinuation (i.e., date of last dose of study drug) in either treatment group will be assumed to follow a similar trajectory to those in the placebo group. All missing data including missing data due to intercurrent events will be handled using the same methodology described in [Section 8.3.1](#), the MNAR statement together with the MODEL option from the SAS[®] MI procedure will be used to impute missing data based on the placebo treatment group only.

The same model used for the primary analysis will then be applied to the imputed datasets.

For this sensitivity analysis the data including imputed values, and associated change from baseline and percent change from baseline values will be summarized by visit.

2. Tipping point analysis (O’Kelly 2014). This will assume that the missing values at least possibly related to a subject’s PMM deviate by a certain amount, delta, in a worsening direction. All values will be imputed using multiple imputation (i.e., MAR) and then a sequential series of analyses will be performed where a value delta is subtracted from the imputed values for those possibly related to PMM. The range of delta will be applied in increments of 5. If it exists, the delta that turns the conclusion from favouring one group to favouring the other is called the tipping point.

A check will be made to ensure the adjusted imputed value is plausible i.e., ≥ 0 , and if not, the value will be fixed at zero. The same model used for the primary analysis will then be applied to the imputed datasets.

For this analysis, a table giving results for each progressively increasing delta value will be produced for Weeks 12 and 24. A forest plot of the estimate of the treatment difference and associated 95% confidence interval for each delta incremental value will also be presented for Weeks 12 and 24.

3. ANCOVA. If the primary analysis model described above does not converge then ANCOVA will be used as the main analysis. However, if the model does converge then as an additional sensitivity analysis the ANCOVA approach will be used to analyse the change from baseline at Week 12 and Week 24 separately. As above, the ANCOVA model will include a fixed term for treatment and the mutation stratification factor and continuous baseline distance walked during the 12MWT as covariates.

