Missing PROMIS T-scores as a result of an intercurrent event considered related to a subject's PMM or study treatment will also be imputed using worst case imputation. A blinded Reneo team will adjudicate these cases.

A blinded Reneo team will also adjudicate whether the subject stops their 30STS test prematurely for reasons at least possibly related to their PMM.

Adjudication decisions will be made and documented prior to database locking and the randomization being unblinded.

Missing data

Missing data may arise for the following reasons:

- Withdrawal from the study
- Specifically, for the 12MWT and 30STS; unwilling or unable to perform the test or walk for the full 12 minutes due to reasons unrelated to their PMM or study treatment

The reasons for not performing a test or stopping it prematurely will be collected. Only reasons which clearly indicate that it was unrelated to the subject's PMM or study treatment will be assigned unrelated. The following are examples of why the reason may be regarded as unrelated to the subject's PMM:

- Site is unable to perform the test at the visit
- Subject suffers an accidental injury prior to the visit with clear evidence the subject's PMM and study treatment did not contribute to the injury
- Unexpected fire alarm at the study center means the test has to be aborted

The independent blinded adjudication committee will review all reasons for missing or incomplete 12MWTs and adjudicate whether the reason was related to the subject’s PMM or study treatment. The committee will also adjudicate whether a subject is unable or unwilling to perform a test.

Missing data assessed as unrelated to a subject’s PMM or study treatment will be considered missing at random (MAR). Missing scores (as opposed to intercurrent events) will be handled using either multiple imputation or through mixed effect models for repeated measures (MMRM). Where multiple imputations are used along with imputations for intercurrent events, the multiple imputation step will be performed prior to imputations for intercurrent events. Hence, the MAR imputations will be replaced with those for intercurrent events where applicable.

The table below summarizes the imputation used for the intercurrent and missing data scenarios for the 12MWT:

Type	Case	Handling of Data
Intercurrent Event	Discontinuation of study treatment only; 12MWT still completed	No imputation required. Use 12MWD recorded

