	Unable to perform the test for reasons possibly related to PMM or study treatment. Subject is not ambulatory at time of assessment.	0
	Unable to walk the full 12 minutes for reasons possibly related to PMM or study treatment*	Use 12MWD recorded
	Ambulatory subject unwilling to, or prevented from, performing the test for reasons possibly related to PMM or study treatment	Worst case multiple imputation
	Withdrawal from study for reasons possibly related to PMM or study treatment	Worst case multiple imputation
	Death	0
Missing Data	Unable to perform the test, or walk the full 12 minutes, for reasons unrelated to PMM or study treatment e.g., COVID-19	Multiple imputation (MAR cases)
	Unwilling to perform the test for reasons unrelated to PMM or study treatment	
	Withdrawal from study unrelated to PMM or study treatment	

* Note: This is the only adjudication decision where the distance walked for subject’s unable to walk the full 12 minutes is used in the analyses. For all other decisions the distance is set to missing prior to analyses.

Multiple Imputation

Missing values will be imputed with the SAS[®] MI procedure. Prior to imputation the missing data pattern will be assessed. To account for non-monotone missingness (i.e., for the 12MWT this would be where a subject has missing data for Week 12, but has data for Week 24), a Markov Chain Monte Carlo (MCMC) model will be used to impute the non-monotone missing data, followed by a sequential regression model to impute the remaining data. Randomization seed numbers will be specified for each part of the imputation to ensure consistency and repeatability.

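### The tipping-point analyses shift only PMM-related values, name no arm, never grade the MAR assumption, and define tipping as reversal rather than loss of significance

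*SAP*

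**What the plan says.** SAP 10.1.4 item 2 (12MWD) works in this order:

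- Start from MAR: "All values will be imputed using multiple imputation (i.e., MAR").
- Then "a sequential series of analyses will be performed where a value delta is subtracted from the imputed values for those possibly related to PMM". Delta rises in steps of 5, with no upper limit and no arm stated.
- A shifted value must be at least 0 m, "and if not, the value will be fixed at zero".
- As to the criterion, "the delta that turns the conclusion from favouring one group to favouring the other is called the tipping point".
- The results at each delta are tabulated for both post-baseline 12MWD visits, with a plot: "A forest plot of the estimate of the treatment difference and associated 95% confidence interval for each delta incremental value will also be presented".

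SAP 8.3.1 fixes what the primary analysis does with the same data. Its table sends "Withdrawal from study for reasons possibly related to PMM or study treatment" to worst-case imputation. A non-ambulatory subject, or one who dies, gets 0 m. By contrast, "Withdrawal from study unrelated to PMM or study treatment" is handled by MAR multiple imputation. The text states the general rule: missing data judged unrelated to "PMM or study treatment will be considered missing at random (MAR").

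SAP 10.2.1 repeats the design for the PROMIS T-score. Delta is added in steps of 5 to PMM-related values, and values are limited to 30.3–83.6.

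Protocol 8.5.1 described a tipping-point analysis over the missing data, with no PMM restriction. SAP Section 14 does not list the narrowing as a change.

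**The concern.** A tipping-point analysis should show how far the missing-data assumption behind the primary result can be bent before the conclusion fails. This one has three gaps.

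1. **Target.** Delta is applied to values that the primary analysis does not treat as MAR. The values it does treat as MAR stay fixed at every step.
2. **Arm.** The natural reading is one delta in both arms. With similar related shares the shift nearly cancels. If placebo has the larger share, it moves the result towards REN001.
3. **Criterion.** Reversal of direction is a much weaker test than loss of significance, and the 0 m floor (or the 83.6 ceiling) can make reversal impossible.

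The study report could therefore state that no tipping point was found when significance had already gone, or when the MAR assumption had not been graded at all. SAP 3.3.1 calls the study pivotal, and these two endpoints form the whole testing sequence (SAP 8.2).

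**Working it through.** **Design figures (SAP 3.5).** Difference 60 m, SD 125 m, two-sided 5%, 93 per arm, about 200 randomized. These reproduce: the noncentral t gives 90.3% power at 93 per arm and 89.9% at 92.

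**Significance versus reversal, ignoring the floor.** With 93 per arm, SE = 125 × √(2/93) = 18.3 m, so significance goes below 1.96 × 18.3 = 35.9 m. From 60 m that is a drop of 24.1 m, while reversal needs 60 m. The written criterion needs a delta 60/24.1 ≈ 2.5 times larger.

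**Assumptions for the rest.** The documents give no missing-data shares, baseline means or worst change. Assumed: 100 per arm; baseline normal, centred on 550, 650 or 750 m, SD 150 m, truncated to 50–1000 m; change N(D, 125) on REN001 and N(0, 125) on placebo. Shifted Week 24 value = max(0, baseline + change − delta). z = difference / √((varA + varP)/100). Delta is scanned in 5 m steps. Between-imputation variance and covariate adjustment are ignored. Results are given as ranges over the three baselines.

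**(a) Common delta, equal related share q, D = 60 m.** At a large delta every shifted value is 0 m, so its change is minus baseline in both arms and those terms cancel. The lowest possible difference is (1 − q) × D, which is always positive.

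| q | Lowest difference | Significance lost at | Reversal |
|---|---|---|---|
| 3.5% | 0.965 × 60 = 57.9 m | not reached | never |
| 7% | 0.93 × 60 = 55.8 m | 725–785 m; not reached at baseline 550 m | never |
| 10% | 0.90 × 60 = 54.0 m | 595–655 m | never |

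**(b) REN001-only delta on the same values, D = 60 m.** At the floor the difference is (1 − q)D − q × baseline, so reversal requires q > D/(D + baseline): 60/610 = 9.8%, 60/710 = 8.5%, 60/810 = 7.4%.

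- q = 7%: significance is lost at 315–320 m. There is no reversal by 1000 m, where about 5–17 m remains.
- q = 10%: significance is lost at 230–235 m, and reversal comes only at about 620–850 m.

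**(c) The test that is not planned.** Related cases stay at worst case in both arms (3.5% each, mean change −200 or −400 m, SD 125 m, floored at 0 m). A REN001-only delta is put on the unrelated, MAR-imputed share u.

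| D | Starting z | u = 2%, lost at | u = 3.5%, lost at |
|---|---|---|---|
| 60 m | about 2.8–3.1 | 705 m or more, or not reached | 420–550 m (3.4–4.4 SD) |
| 45 m | about 2.1–2.3 | about 135–315 m | 80–190 m (0.6–1.5 SD) |

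A 45 m result is within the significant range, because with 100 per arm the smallest significant difference is 1.96 × 125 × √(2/100) = 34.6 m.

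**(d) PROMIS.** Assumed: difference 3 points, baseline T-score N(60, 7), change SD 6, 8 or 10, 100 per arm, cap 83.6, REN001-only delta. Significance is lost at 20, 15 and 5 points respectively at a 7% share, and at 15, 10 and 5 points at 10%. The cap then blocks reversal at any delta, with roughly 1 point left at 7% and 0.3 at 10%. At 15% the result reverses at 25 points.

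**The case against.** The best counter-argument is that little informative missingness is left in the MAR group. SAP 8.3.1 assigns a case as unrelated only on clear evidence, with examples such as a fire alarm or a site that cannot run the test. For 12MWD an independent blinded committee decides, and decisions are documented before unblinding. Doubtful cases already receive 0 m or a worst-case draw. Read this way, item 2 has a purpose of its own: it asks whether the result depends on that harsh handling. This lowers the risk but does not remove it, because withdrawals judged unrelated still enter as MAR.

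The MAR values are also stressed elsewhere. For 12MWD, the all-cause worst case (10.1.5 item 4) replaces every missing value, and the placebo-based pattern mixture (10.1.4 item 1) covers missing data after discontinuation. Both are single fixed scenarios and do not show how large a departure overturns the result. PROMIS has the pattern mixture but lists no all-cause worst case.

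Confidence intervals at each delta do let a reader see loss of significance, but only for the scenarios that are run.

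Equal shares are the setting least favourable to the SAP. With unequal related shares a common delta is informative: under the same model, 10% against 5% loses significance at about 350 m, and 15% against 5% at about 215 m, with reversal beyond 600 m. That is fair, but it makes the result depend on an imbalance that the plan does not control.

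PROMIS is not among the assessments at off-drug Week 12 and 24 visits (SAP 3.4, footnote 4), so more of it may be missing. It is collected at Early Termination, and that value can fall in a visit window, but this does not help subjects who stop well before Week 24.

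Finally, at the 60 m design effect the MAR assumption would usually look robust.

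**Conclusion.** The concern holds for both endpoints and should be fixed. All three gaps are visible in the wording and need no assumed numbers: delta misses the MAR values, no arm is named, and tipping means reversal. That reversal is impossible under a common delta, equal shares, balanced baselines and the 0 m floor is algebra.

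The deltas at which significance is lost do rest on assumed shares, baselines and worst change, and for PROMIS also on an assumed effect and SD. They indicate scale only. The practical weight is greatest for a significant 12MWD difference well below 60 m, where a departure of about 0.6–1.5 SD in 3.5% of one arm could undo the result unseen. The primary estimate, its test and the type 1 error are not affected.

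**What to change.** In SAP 10.1.4 item 2 and SAP 10.2.1 sensitivity item 2:

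- Keep the primary handling of related intercurrent events.
- Apply delta to the MAR-imputed, unrelated values in the REN001 arm with placebo delta = 0, or use a two-way grid of arm-specific deltas.
- Define the tipping point as the smallest delta at which the two-sided p-value exceeds 0.05.
- If wanted, keep the present grid on related values as a second analysis, also with arm-specific deltas.
- As a wording clarification, align PMM with PMM or study treatment; SAP 8.3.1 uses both for the same rule.

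The cost is SAP wording, a small change to the imputation macro and some extra output, with no new data. The reported tipping point may look less favourable.

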10.1.5. Supplementary Analyses

The following supplementary analyses will be performed for the primary endpoint:

1. Per protocol analysis. The primary analysis will be repeated for the PP analysis set.

2. While on-treatment strategy. Only on-treatment values (up to 7 days after the subject's last dose of study drug) will be considered for analysis; consequently, only subjects in the mFAS will be included. For this strategy the estimand is defined as the difference in means between the treatments in the target population for the change from baseline in 12MWD, while the subject continues to receive study drug (plus 7 days).

The last on-treatment change from baseline in 12MWD will be analysed using an ANCOVA. The model will include a fixed term for treatment and the mutation stratification factor and continuous baseline distance walked during the 12MWT as covariates. The treatment comparison will be estimated, along with its standard error, 95% confidence interval and associated p-value.

3. Treatment period restricted analysis. On-treatment values will be analysed for the mFAS. This analysis restricts the observation time of interest to the time of last dose of study drug plus 7 days. For this strategy the estimand is defined as the difference in means between the treatments in the target population for the change from baseline at Week 24 in 12MWD, while the subject continues to receive study drug (plus 7 days).

The same model used for the primary analysis will be applied. All missing data will be assumed MAR and predicted from the MMRM model without multiple imputation.

4. Worst case imputation. This will impute all missing data irrespective of cause using a worst case imputation as described in [Section 8.3.1](#). The same model used for the primary analysis will then be applied to the imputed datasets. The data including imputed values, and associated change from baseline and percent change from baseline values will be summarized by visit.

5. Non-parametric analysis. All missing data including missing data due to intercurrent events will be handled using the same methodology described in [Section 8.3.1](#). A Hodges-Lehmann estimate ('Interval midpoint') and asymptotic standard error will be calculated for change from baseline, taking account of the variables; stratification mutation factor and categorical baseline distance walked during the 12MWT. The estimates will then be combined across the imputations to give a pooled estimate of treatment effect which will be presented together with the asymptotic standard error, 95% confidence interval and associated p-value.

A review of baseline blinded data revealed that the number of subjects in the ≤ 500 m baseline 12MWD is small. Consequently, to improve the balance of subjects across the strata groups in the analysis the categories for baseline 12MWD will be ≤ 650 m and >650 m.

10.1.6. Subgroup Analyses

The impact of all subgroups (specified in [Section 8.5](#)) on the primary endpoint will also be investigated descriptively. Summaries will be presented by subgroup and the imputed

datasets generated for the primary analysis will be analysed by subgroup using the primary analysis model. A forest plot of the estimate of the treatment difference and associated 95% confidence interval for each subgroup will be presented for Weeks 12 and 24.

10.2. SECONDARY ENDPOINT

10.2.1. Patient-Reported Outcomes Measurement Information System (PROMIS) Short Form – Functional Assessment of Chronic Illness Therapy (FACIT) Fatigue 13a

Intercurrent events and missing data will be handled using the methodology described in [Section 8.3.1](#). Missing values will be imputed using the technique of multiple imputations. Missing data as a result of an intercurrent event which is considered related to a subject's PMM will be imputed using worst case imputation. The multiple imputation step will be performed prior to any imputations for intercurrent events.

Changes from baseline in T-score will be analysed using a MMRM. The model will include fixed terms for treatment, visit and the treatment-by-visit interaction. The model will also include the stratification mutation factor, continuous baseline score and continuous baseline distance walked during the 12MWT as covariates. An unstructured covariance structure will be used, and the model will allow the covariance matrix to differ between treatment groups. If this analysis fails to converge, then an analysis of covariance (ANCOVA) will be used which will analyse the change from baseline at each post-baseline visit separately. The ANCOVA model will include a fixed term for treatment and the mutation stratification factor, continuous baseline score and continuous baseline distance walked during the 12MWT as covariates. The Kenward-Rogers approximation will be used to estimate the denominator degrees of freedom. The treatment comparison for the change from baseline at each visit will be estimated. The estimates, standard errors, 95% confidence intervals and associated p-values will be presented for each visit. The estimates, standard errors, 95% confidence intervals and associated p-values will be presented for each of the multiple imputation analyses as well as the pooled values.

Observed and change from baseline values will be summarized by visit, both including and excluding imputed values. The imputed summary statistics will be based on Rubin's methodology ([Rubin 1987](#)) to combine the means and standard errors from the imputed data sets. The associated 95% confidence intervals for the observed and change from baseline means will also be presented.

Mean plots of observed and changes from baseline values, with 95% confidence intervals, will be presented by treatment group with visit on the x-axis. A reference line for no change (i.e., y=0) will be included in the change from baseline plot.

Spaghetti plots for the changes from baseline will be plotted over time. The plots will be split by treatment group. The y-axis will be uniform across the plots to allow comparisons. A reference line for no change (i.e., $y=0$) will be included.

Categorical shift tables of change from baseline showing improvement (at least a 5-point decrease in score), no change (less than a 5-point change in either direction) or worsening (at least a 5-point increase in score) at each visit will be summarized. The table will include categories for withdrawn and missing. Percentages will not be presented for the withdrawn and missing rows, and the percentages presented will use the number of non-missing values as the denominator. In addition, to account for subjects at the extreme ends of the scale, the shift table will also include the percent improving or worsening based on those subjects who have the potential to improve or worsen respectively.

Sensitivity Analyses

A pattern mixture multiple imputation and tipping point analysis similar to the primary analysis will also be performed.

1. Pattern mixture multiple imputation. This will assume that missing data after treatment discontinuation in either treatment group will be assumed to follow a similar trajectory to those in the placebo group.

Missing data will be imputed using multiple imputation as defined in [Section 8.3.1](#), the MNAR statement together with the MODEL option from the SAS[®] MI procedure will be used to impute missing data based on the placebo treatment group only. The same model used above will then be applied to the imputed datasets and the SAS[®] MIANALYZE procedure will be used to produce pooled estimates of the treatment difference, along with their standard errors, 95% confidence intervals, and associated p-values.

For this sensitivity analysis the data including imputed values, and associated change from baseline will be summarized by visit.

2. Tipping point analysis. This method assumes that the missing values at least possibly related to a subject's PMM deviate a certain amount, delta, in a worsening direction. Missing data will be imputed using multiple imputation (i.e., MAR) as defined in [Section 8.3.1](#); then a sequential series of analyses will be performed where a value delta is added to the imputed values for those related to PMM. The delta will be applied in increments of 5 which is equivalent to half a standard deviation based on a US population. If it exists, the delta that turns the conclusion from favouring one group to favouring the other is called the tipping point.

A check will be made to ensure the adjusted imputed value is plausible i.e., ≥ 30.3 and ≤ 83.6 , and if not, the value will be fixed at either 30.3 or 83.6 respectively. The same model used for the main analysis above will then be applied to the imputed datasets.

For this analysis, a table giving results for each progressively increasing delta value will be produced for each visit. A forest plot of the estimate of the treatment difference and associated 95% confidence interval for each delta incremental value will also be presented for each visit.

3. ANCOVA. If the primary analysis model described above does not converge then ANCOVA will be used as the main analysis. However, if the model does converge then as an additional sensitivity analysis the ANCOVA approach will be used to analyse the change from baseline at each post-baseline visit separately. The ANCOVA model will include a fixed term for treatment and the mutation stratification factor, continuous baseline score and continuous baseline distance walked during the 12MWT as covariates.

Supplementary Analyses

The following supplementary analyses will be performed:

1. Per protocol analysis. The analysis will be repeated for the PP analysis set.
2. While on-treatment strategy. Only on-treatment values (up to 7 days after the subject's last dose of study drug) will be considered for analysis; consequently, only subjects in the mFAS will be included. This analysis will take the last value prior to discontinuation of study treatment.

The last on-treatment change from baseline will be analysed using an ANCOVA. The model will include a fixed term for treatment and the mutation stratification factor, continuous baseline score and continuous baseline distance walked during the 12MWT as covariates. The treatment comparison will be estimated, along with its standard error, 95% confidence interval and associated p-value.

3. Treatment period restricted analysis. On-treatment values will be analysed for the mFAS. The same model used for the main analysis will be applied. All missing data will be assumed MAR and predicted from the MMRM model without multiple imputation.
4. Non-parametric analysis. All missing data including missing data due to intercurrent events will be handled using the same methodology described in Section 8.3.1. A Hodges-Lehmann estimate ('Interval midpoint') and asymptotic standard error will be calculated for change from baseline, taking account of the variables:
 - a. Stratification mutation factor
 - b. Categorical baseline T-score (≤ 60 and > 60)

The estimates will then be combined across the imputations to give a pooled estimate of the treatment effect which will be presented together with the asymptotic standard error, 95% confidence interval and associated p-value.

As for the primary endpoint, the impact of all subgroups (specified in [Section 8.5](#)) will also be investigated descriptively. Summaries will be presented by subgroup and the imputed datasets generated for the main analysis will be analysed by subgroup using the main analysis model. A forest plot of the estimate of the treatment difference and associated 95% confidence interval for each subgroup will be presented for Weeks 12 and 24 only.

